6.3. Other Endpoints

- Δ DAS28-3 (CRP) at all time points (see [Appendix 2.3](#)).
- HAQ-DI response, defined as an improvement (ie, a decrease) from baseline of ≥ 0.30 and ≥ 0.35 (2 endpoints) in HAQ-DI scores at all timepoints (see [Appendix 2.2](#)).
- ACR response criteria components (Δ in following: HAQ-DI, CRP, Patient's Assessment of Arthritis Pain, Patient's Global Assessment of Arthritis, Physician's Global Assessment of Arthritis, swollen joint count, tender/painful joint count) at all time points (see [Appendix 2.1](#)). Note that Δ HAQ-DI is covered under [Section 6.2](#) as a secondary endpoint already.
- *Psoriatic Arthritis Joint Activity Index (raw PsAJAI)* (see [Appendix 2.5](#)), *Disease Activity Index for Reactive Arthritis/PsA (Δ DAREA/DAPSA)* (see [Appendix 2.6](#)), *Composite Psoriasis Disease Activity Index (Δ CPDAI)* (see [Appendix 2.7](#)), *Psoriatic Arthritis Disease Activity Score (Δ PASDAS)* (see [Appendix 2.9](#)), *Minimal Disease*

Activity (MDA, yes/no) and their components (yes/no response for each component) (see [Appendix 2.8](#)) at all time points.

- BSA (% Δ BSA) at all time points (see [Appendix 2.10](#)).
- Presence of dactylitis at all time points.
- Nail Psoriasis Severity Index (Δ NAPSI) Score at Month 1, Month 6 (and every 6 months thereafter).

This is a score ranging from 0-8 based on 1 targeted nail.

- Itch Severity Item (Δ ISI) at Month 1, Month 6 (and every 6 months thereafter) (see [Appendix 2.13](#)).
- Patient's Global Joint and Skin Assessment (Δ PGJS-VAS, 3 endpoints) at all time points.
- Ankylosing Spondylitis Quality of Life questionnaire (Δ ASQOL) at all time points.

The ASQOL has a total score which is calculated by summing the 18 items.

- Physical function/other patient reported outcomes to be assessed at Month 1, Month 6 (and every 6 months thereafter): Dermatology Life Quality Index (Δ DLQI); PsA Healthcare Resource Utilization Questionnaire (raw PsA HCRU and Δ PsA HCRU-Self Rating of Job Performance at Work); Work Limitations Questionnaire (Δ WLQ).

A total score for DLQI is computed from 10 questions.

The WLQ is a twenty-five item scale that evaluates the degree to which health problems interfere with an ability to perform job roles along four dimensions. The Time Management scale (Question 1) contains five items. The Physical Demands scale (Question 2) contains 6 items. The Mental/Interpersonal Demands Scale (Questions 3 and 4) has nine items. The Output Demands scale (Question 5) contains five items. Scores for each item are: 0 (none of the time), 1, 2, 3 or 4 (all of the time). "Does not apply to my job" is treated as missing. Each of the scale scores are computed by averaging the items that comprise the scale, and then multiplying by 25.

- Incidence of investigator-reported clinically significant changes in physical examination from baseline (in this and/or prior study) during treatment.
- Incidence of electrocardiogram (ECG) abnormalities and change from baseline (in this and/or prior study) in ECG measurements during treatment.
- Incidence of vital sign (blood pressure and pulse rate) abnormalities and changes from baseline (in this and/or prior study) in vital sign measurements during treatment.

6.4. Covariates

Reporting of the study data will be done with descriptive statistics. There will be no statistical models, and hence no covariates.

7. HANDLING OF MISSING VALUES

For the SF-36v2, ASQOL, DLQL, EQ-5D-3L, BASDAI, WLQ, PsA-HCRU, and FACIT-F instruments, rules suggested by the developers of these will be followed in calculating scores when individual question/items may be missing. If these rules are not enough for calculating a score, then the endpoint will be considered to have a missing value. Missing values in any of the endpoints will not be imputed when summarizing these endpoints using descriptive statistics. See [Appendix 2](#) for additional details for the calculation of endpoints, including handling of missing item values in the calculation.

8. STATISTICAL METHODOLOGY AND STATISTICAL ANALYSES

There will be 2 sets of analyses: one for the A3921092 LTE and the other for the sub-study. For the A3921092 LTE, the safety analysis will include cumulative data from all the subjects and all the data (including the data collected in the sub-study). The efficacy analysis for the LTE will only include the data collected in the A3921092 LTE (the efficacy data collected in the sub-study will be excluded from the LTE analysis).

Statistical methods for the sub-study are found in [Appendix 6](#).

8.1. Statistical Methods

8.1.1. Analyses for Continuous Data

In general, the data for all continuous endpoints will be summarized by time point in tables containing descriptive statistics (N, mean, standard deviation, standard error of the mean, minimum, 1st, 2nd (median) and 3rd quartiles and maximum) for baseline and change from baseline for those endpoints measured at baseline.

8.1.2. Analyses for Categorical Data

The data for all categorical endpoints (including binary) will be summarized by contingency tables that show the counts/frequency in the various categories at each time point. For some categorical endpoints, such as the presence or severity of adverse events, contingency or frequency tables will consider the data over the entire duration of the study and will not be constructed at each time point.

Normal approximation will be used for the construction of confidence interval (CI) for the responder rate over time. Let N be number of subjects assessed at each visit and n be number of responders, and $p_{\text{obs}} = n/N$ be the observed responder rate, then the two-sided 95% CI will be formed by $p_{\text{obs}} \pm 1.96 \times \text{squared root of } [p_{\text{obs}} \times (1 - p_{\text{obs}}) / N]$.

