9.1. Sample Size Determination

The sample size of this study is determined by the number of subjects who enroll from qualifying randomized PsA studies with tofacitinib.

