5.4. Other Analysis Sets

5.4.1. Endpoint Specific Analysis Sets

Subjects will be excluded from FAS for analyzing a specific endpoint if the criterion for inclusion is not met for the endpoint as described in

Table 1.

Table 1 Endpoint Specific Analysis Sets

Instrument/Endpoint	Inclusion	Rationale
PASI75 or PASI	Include subjects with baseline BSA \geq 3% and baseline PASI $>$ 0	PASI is not assessed if baseline BSA $<$ 3% per the study protocol; PASI=0 means absence of psoriasis as measured by PASI.
Δ PGA-PsO	Include subjects with baseline PGA-PsO $>$ 0	PGA-PsO=0 means no PsO disease at baseline as measured by PGA.
Δ BSA	Include subjects with baseline BSA $>$ 0%	BSA=0% means no PsO disease at baseline as measured by BSA.
HAQ-DI responder (decrease Δ HAQ-DI \geq 0.30)	Include subjects with baseline HAQ-DI \geq 0.30	Restrict baseline HAQ-DI to \geq 0.30 to allow room for response
HAQ-DI responder (decrease Δ HAQ-DI \geq 0.35)	Include subjects with baseline HAQ-DI \geq 0.35	Restrict baseline HAQ-DI to \geq 0.35 to allow room for response
Dactylitis presence	Include subjects with baseline DSS $>$ 0	Baseline DSS=0 means absence of dactylitis. Dactylitis is not an enrollment criterion so it is expected that only a subset of the subjects will have dactylitis at baseline.
Δ DSS	Include subjects with baseline dactylitis severity score (DSS) $>$ 0	Baseline DSS=0 means absence of dactylitis. Dactylitis is not an enrollment criterion so it is expected that only a subset of the subjects will have dactylitis at baseline.
Δ Leeds Enthesitis Index (Δ LEI)	Include subjects with baseline LEI $>$ 0	Baseline LEI score=0 means absence of enthesitis as measured by LEI. Enthesitis is not an enrollment criterion so it is expected that only a subset of the subjects will have enthesitis at baseline.
Δ SPARCC Enthesitis Index	Include subjects with baseline SPARCC Enthesitis Index $>$ 0	Baseline SPARCC Enthesitis Index score=0 means absence of enthesitis as measured by SPARCC. Enthesitis is not an enrollment criterion so it is expected that only a subset of the subjects will have enthesitis at baseline.
Δ BASDAI	Include subjects with presence of spondylitis at screening and baseline BASDAI score $>$ 0 cm	Absence of spondylitis at screening or baseline BASDAI score=0 cm means absence of spondylitis. Spondylitis is not an enrollment criterion so it is expected that only a subset of the subjects will have spondylitis at baseline.

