7.1.2. Analyses for Categorical Data

The data for all categorical endpoints (including binary) will be summarized by contingency tables that show the counts/frequency of the response at each visit by treatment group. For some categorical endpoints, such as the presence or severity of adverse events, contingency or frequency tables will consider the data over the entire duration of the study and will not be constructed at each time point.

Two-sided p-value and 95% CI will be generated by normal approximation to the binomial distribution approach for the treatment comparison between the 2 groups. Let N be number of subjects assessed at each visit, n be number of responders, and $\hat{p} = n/N$ be the observed responder rate. Use subscript t to refer to the treatment group (Tofacitinib + Placebo) and c to refer to the treatment group (Tofacitinib + MTX). Then the normal approximation to the 2-sided p-value will be calculated as

$$2Pr\left\{Z \geq \left| \frac{\hat{p}_t - \hat{p}_c}{\sqrt{\frac{\hat{p}_t(1-\hat{p}_t)}{N_t} + \frac{\hat{p}_c(1-\hat{p}_c)}{N_c}}} \right| \right\},$$

where Z is Normal (0, 1) distributed.

Two-sided 95% CI will be formed by

$$(\hat{p}_t - \hat{p}_c) \pm 1.96 \sqrt{\frac{\hat{p}_t(1-\hat{p}_t)}{N_t} + \frac{\hat{p}_c(1-\hat{p}_c)}{N_c}}.$$

If there is no (ie, 0) response or 100% response in any of treatments, 0.5 will be added to the number of responses and 1 will be added to the denominator in each treatment corresponding to the pair of comparison for calculating the treatment difference, standard error, 95% CI and 2-sided p-value (Agresti, 2002).

When response rate of 0% or 100% is observed in both treatments in comparison, no formal comparison will be performed. Estimated response rate of 0% or 100% will be reported as observed.

The final results will be expressed in percentages, ie, (proportions x 100)%.

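### The LTE responder-rate interval is a plain Wald interval with no rule for 0% or 100%: it collapses to zero width there and can under-cover if a visit-level N is small or the rate extreme

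*SAP*

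**What the plan says.** SAP 8.1.2 covers categorical data in the LTE: "Normal approximation will be used for the construction of confidence interval (CI) for the responder rate over time". It defines the terms ("Let N be number of subjects assessed at each visit and n be number of responders") and gives the two-sided 95% limits as the observed rate plus or minus 1.96 times the square root of p(1−p)/N. It has no provision for an observed rate of 0% or 100%.

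Three other provisions determine which N enters the formula.

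- SAP 7: "Missing values in any of the endpoints will not be imputed when summarizing these endpoints using descriptive statistics". N is therefore the number of subjects with a non-missing value at that visit.
- SAP 5.4.1 drops a subject from an endpoint's analysis when that endpoint's entry condition in Table 1 is failed. Four rows of that table are binary endpoints: PASI75 (baseline BSA at least 3% and PASI above 0), HAQ-DI decrease of at least 0.30, HAQ-DI decrease of at least 0.35, and dactylitis presence. For dactylitis the SAP adds: "Dactylitis is not an enrollment criterion so it is expected that only a subset of the subjects will have dactylitis at baseline". ACR20/50/70, PsARC and MDA use the full analysis set.
- Protocol 9.1: "The sample size of this study is determined by the number of subjects who enroll from qualifying randomized PsA studies with tofacitinib". No number is given.

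The sub-study section (SAP Appendix 6, 7.1.2) also uses a normal approximation, for the difference between two arms, but it includes a boundary rule: "If there is no (ie, 0) response or 100% response in any of treatments, 0.5 will be added to the number of responses", with 1 added to the denominator in each arm.

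**The concern.** The Wald interval takes its width from the observed rate. When every assessed subject responds, or none does, the estimated standard error is zero and the output is a 95% interval of 100% to 100% or 0% to 0%. Read literally, that claims certainty, whatever N is. Close to the boundary the limits can pass 0% or 100%. The SAP deals with the boundary in one part and is silent on it in the other.

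The second issue is coverage. The normal approximation is weak when few subjects are assessed or the true rate is near 0% or 100%. The plan contains several mechanisms that lower N at later visits: no imputation, baseline-restricted sets, ACR rates split by qualifying study (SAP 8.2.2), data-cuts (SAP 3), and transfer of subjects to the sub-study from Month 24, after which their efficacy data leave the LTE analysis (Protocol 6.2.2 to 6.2.4; SAP 8). The LTE has no comparator and no tests, so this interval is the only stated measure of uncertainty for a responder rate.

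**Working it through.** **Inputs.** From SAP 8.1.2: the formula, the multiplier 1.96, two-sided 95%, and N as subjects assessed. The two-sided 5% normal quantile is 1.95996, which reproduces the stated 1.96. The documents give neither N nor the true rate p for any LTE responder endpoint, so both are assumed over a range below. Coverage at p equals coverage at 1−p.

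**Step 1: the boundary (no assumption needed).** If n = N, then p_obs = 1, sqrt[1×0/N] = 0, and the interval is [100%, 100%]. If n = 0 it is [0%, 0%]. For comparison, the Wilson lower limit at N/N is 83.9% (N=20), 88.6% (N=30), 92.9% (N=50) and 96.3% (N=100).

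**Step 2: limits outside the range.** For 19/20: sqrt(0.95×0.05/20) = 0.0487; 1.96×0.0487 = 0.0955; limits 85.4% to 104.6%. Wilson gives 76.4% to 99.1%.

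**Step 3: exact coverage.** Coverage = sum over n of P(n | N, p) × [1 if p lies in the interval computed from n, otherwise 0].

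- *N=20, p=5%.* The interval contains 5% only for n = 1 to 4. P(n=0) = 0.95^20 = 0.358 and P(n≥5) = 0.003, so coverage = 1 − 0.358 − 0.003 = 0.639. The zero-width interval itself occurs 35.8% of the time.
- *N=30, p=10%.* At n=1 the upper limit is 9.8%, so n=1 misses as well as n=0. P(n≤1) = 0.184 and P(n≥8) = 0.008; coverage = 0.809.
- *N=100, p=5%.* At n=2 the upper limit is 4.7%, so n = 0 to 2 all miss. P(n≤2) = 0.118 and P(n≥12) = 0.004; coverage = 0.877.

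| Assumed N, p | Wald (as planned) | Wald + sub-study rule | Wilson | Clopper-Pearson |
|---|---|---|---|---|
| 20, 5% | 63.9% | 99.7% | 92.5% | 98.4% |
| 30, 10% | 80.9% | 80.9% | 97.4% | 99.2% |
| 50, 10% | 87.9% | 87.9% | 97.0% | 97.0% |
| 100, 5% | 87.7% | 87.7% | 96.6% | 98.3% |

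**Step 4: would the sub-study rule be enough?** At n=0 and N=30 it uses 0.5/31 = 1.6%, with an upper limit of 6.0%, which still misses a true 10%; n=1 is untouched. At 30/30 it gives 94.0% to 102.8%. It removes the zero width, but it leaves coverage unchanged in three of the four cases and leaves a limit above 100%.

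**Step 5: moderate rates.** Over true rates of 30–70%:

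| N | Mean Wald coverage | Minimum |
|---|---|---|
| 10 | 89.2% | 84.0% |
| 20 | 92.3% | 88.6% |
| 30 | 93.5% | 91.1% |
| 50 | 93.9% | 92.1% |
| 100 | 94.3% | 93.4% |
| 200 | 94.6% | 94.0% |

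Over rates of 10–90%, the minimum at N=100 is 92.1%. Marked under-coverage therefore needs N of about 10, or a rate near 0% or 100% with N up to roughly 50–100.

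**The case against.** The strongest reply is that nothing shows the extreme cases will arise. Table 1 of the SAP gives criteria, not sizes, and no LTE responder rate is predicted. The nearest figure, in Protocol 1.2.7, is a model-predicted placebo-adjusted PASI75 response of 50% at 5 mg BID. It comes from psoriasis patients and is not an LTE forecast, but it is mid-range. The cohort also looks large: about 180 subjects are to be randomised into the sub-study after at least 24 months in the LTE, and only those on 5 mg BID with oral methotrexate qualify (Protocol Appendix 10, sections 3 and 4.1). The plan therefore implies at least that many at Month 24, before other regimens are counted. The LTE has no hypotheses or decision rules (SAP 4.1, 4.2), the primary safety analysis does not use this interval, and the required counts would show 0/N or N/N beside any zero-width interval. Dactylitis presence, the likeliest trouble spot, is not called a response, so it may not receive this interval at all.

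Most of this stands. It makes the coverage loss conditional and limits its consequences. It does not touch the boundary defect, which is algebraic, or the difference between the two parts of the SAP. A large cohort at Month 24 also does not fix N for a restricted set at Month 36, after transfers to the sub-study and with missing values left out.

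**Conclusion.** The point holds in two parts of different strength. Without any assumption, the LTE formula gives a zero-width 95% interval at 0% or 100%, can give limits outside 0–100%, and lacks the boundary rule that the same SAP gives the sub-study. Conditionally on assumed N and p, coverage can drop to 64–88%; for N of 50 or more and rates of 30–70% it stays at about 92% or higher and Wald is adequate.

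A reader might infer three stronger things that the documents do not support. One is that the Table 1 sets are small: no size is stated, and the SAP says only that a part of the subjects will have dactylitis. Another is that rates will lie near 0% or 100% after years of treatment: no LTE rate is given, and an approach to 0% for dactylitis is conjecture. The third is that the LTE intervals in general are not 95% intervals: for full-set endpoints at moderate rates the shortfall is a few points at most.

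The restricted binary endpoints concerned are PASI75, the two HAQ-DI responses and, if it receives the interval, dactylitis presence. All are descriptive secondary or other endpoints, so the impact is limited. The change is still worth making because it costs so little.

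**What to change.** In SAP 8.1.2, replace the Wald formula with the Wilson score interval (or Clopper-Pearson, if guaranteed coverage is preferred to shorter intervals) for all LTE responder rates, and state whether dactylitis presence receives an interval. Do not simply import the +0.5/+1 rule from Appendix 6, for the reasons in step 4 of the working.

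The cost is one SAP sentence and a change of interval method in the programming. Point estimates, counts and data collection are unaffected. The intervals become slightly asymmetric around the observed rate, and for large N and moderate rates they barely change.

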8.2. Statistical Analyses

Tofacitinib dose may be increased to 10 mg BID at study visits based upon investigator's discretion. Also, tofacitinib dose may be decreased (ie, 10 mg BID to 5 mg BID) for safety

reasons at any time. Hence changes in the dose are treatment related. Consequently, descriptive statistics will be displayed for just one treatment group: the entire cohort of subjects in which tofacitinib is dosed flexibly between 5 mg and 10 mg BID.

The baseline values for the safety endpoints come from the baseline of the qualifying study for patients who enroll within 14 days of the last visit of the qualifying study. For the patients whose enrollment are out of 14-day window, their baseline values of the safety endpoints will be from the baseline visit of this study, A3921092. The baseline values for all the efficacy or health-outcome endpoints come from the baseline of the qualifying study. In addition, as a sensitivity analysis for the ACR response rates and Δ HAQ-DI, the baseline value will be the baseline visit for A3921092 for patients whose enrollment is out of 14-day window.

All analyses will use FAS (Section 5.1) or FAS with some subjects excluded from analyses for certain endpoints (Section 5.4.1) except where indicated otherwise.

